6.2.12. Overdose of IMP

There is no known antidote to AZD4547. Investigators should be advised that any patient who receives a higher dose of AZD4547 than that intended should be monitored closely, managed with appropriate supportive care and followed up expectantly.

If an overdose of AZD4547 occurs in the course of the study, then Investigators or other site personnel should inform the Sponsor **within one day** i.e. immediately and no later than **the end of the next business day** of when he or she becomes aware of it.

For overdoses associated with a SAE, standard reporting timelines apply. For other overdoses, reporting should be done within 30 days.

For treatment of overdose with anastrozole / letrozole please refer to the local prescribing information. Overdose of anastrozole or letrozole with associated AEs / SAEs should be recorded in the relevant AE / SAE module of the eCRF and reported according to the standard timelines.

6.3. Permanent Discontinuation of Study Medication and Withdrawal from Study

6.3.1. Permanent Discontinuation of Study Medication

A patient may be permanently discontinued from study medication for the following reasons:

- Patient decision
- Significant adverse events or unacceptable toxicities
- Severe non-compliance to this protocol as judged by the Investigator
- Confirmed disease progression
- Allergic reaction to study medication
- If the investigator considers that a subject's health will be compromised due to adverse events or concomitant illnesses that develop after entering the study.

Date of permanent discontinuation and the reason will be recorded.

Once study medication is permanently discontinued it cannot be restarted.

6.3.2. Withdrawal from Study

Withdrawal from the study refers to discontinuation of both study medication and study participation; this can occur at any time according to the following reasons:

- Patient decision
- Lost to follow-up
- Death
- Investigator decision

If a patient dies whilst participating in the study a “Statement of Death” CRF must be completed. The following details will be collected: date of death, whether autopsy performed, whether death was related to the disease under investigation, primary cause of death, secondary cause of death, and any other details.

6.3.3. Procedures for Withdrawal from Study

If the patient is withdrawn from the study the date of withdrawal and the reason must be recorded. If possible, the investigator should arrange for the end of study assessments to be completed. Where the patient has withdrawn due to an AE, the investigator should follow the procedures in section 7.0.

7. PHARMACOVIGILANCE

7.1. Definition of an Adverse Event (AE)

An AE is any untoward medical occurrence (including deterioration of a pre-existing medical condition) in a patient or clinical trial subject administered a medicinal product, and which does not necessarily have a causal relationship with this treatment. An AE can therefore be any unfavourable and unintended sign including abnormal results of an investigation (e.g. laboratory finding, electrocardiogram), symptom(s) (e.g. nausea, chest pain), signs (e.g. tachycardia, enlarged liver) or disease temporally associated with the use of the trial medication.

7.1.1. Disease Progression

Disease progression is a worsening of a patient's condition attributable to the disease for which the study medication is being given. This may be an increase in severity of the disease or increase in the symptoms of the disease. The development of new, or progression of existing metastasis to the primary cancer under study should be considered as disease progression and not an AE. **Events that are unequivocally due to disease progression should not be reported as AEs during the study.**

7.1.2. New Cancers

The development of a new cancer should be regarded as an AE and reported accordingly. Generally, it will also meet at least one of the serious criteria.

7.2. Recording of Adverse Events

AEs will be collected throughout the study, from the point that the RADICAL team have confirmed patient eligibility, via e-mail (and the study entry eCRF has been completed by the RADICAL team) until the end of follow-up; they will be followed up according to local practice until the event has stabilised or resolved, or the Follow-up Visit, whichever is the sooner*. Serious Adverse Events (SAEs) will also be recorded throughout the study.

Any AEs which remain unresolved at the patient's last visit in the study should be followed up by the Investigator for as long as medically indicated, but without further recording in the CRF.*

***N.B. Any ophthalmic AEs will be followed up until event resolution or stabilisation (or until the trial closes if event is on-going at the end of trial) and should be recorded in the eCRF.**

If an Investigator learns of any SAEs, including death, at any time after a patient has completed the study and he/she considers there is a reasonable possibility that the event is related to AZD4547, the Investigator should notify the trials unit.

The following details will be collected in the CRF for each AE:

- AE description / diagnosis
- Date of onset and date of resolution
- CTCAE grade maximum intensity
- Seriousness
- Investigator causality rating against the study medication (yes or no)
- Action taken with regard to study medication
- Outcome

7.3. Severity of Adverse Events

Severity is a measure of intensity whereas seriousness is defined by the criteria in section 7.6. Severity will be assessed using the grading scales found in the National Cancer Institute CTCAE version 4.02 (September 2009) for all adverse events with an assigned CTCAE term. For those events without assigned CTCAE grades, the recommendation on page 1 of the CTCAE that converts mild, moderate and severe into CTCAE grades should be used. A copy of the CTCAE version 4.02 can be downloaded from the Cancer Therapy Evaluation Program website (<http://ctep.cancer.gov>).

7.4. Causality of Adverse Events

The Investigator will assess causal relationship between the investigational product and the combination treatment and each AE.

Unassessable: There is insufficient or incomplete evidence to make a clinical judgement of the causal relationship

Unrelated: No evidence of any causal relationship

Unlikely: There is little evidence to suggest there is a causal relationship (e.g. the event did not occur within a reasonable time after administration of the trial medication). There is another reasonable explanation for the event (e.g. the patient's clinical condition, other concomitant treatment).

Possible: There is some evidence to suggest a causal relationship (e.g. because the event occurs within a reasonable time after administration of the trial medication). However, the influence of other factors may have contributed to the event (e.g. the patient's clinical condition, other concomitant treatments).

Probable: There is evidence to suggest a causal relationship and the influence of other factors is unlikely.

Definite: There is clear evidence to suggest a causal relationship and other possible contributing factors can be ruled out.

7.5. Abnormal Laboratory Test Results

All clinically important abnormal laboratory test results occurring during the study will be recorded as adverse events. The clinically important abnormal laboratory tests will be repeated at appropriate intervals until they return either to baseline or to a level deemed acceptable by the investigator and the clinical monitor, or until a diagnosis that explains them is made.

7.6. Definitions of Serious Adverse Events (SAE)

An SAE is an AE occurring during any part of the study that meets one or more of the following criteria:

- Results in death;
- Is life-threatening*;
- Requires hospitalisation or prolongation of existing inpatient's hospitalisation**;
- Results in persistent or significant disability or incapacity;
- Is a congenital abnormality or birth defect;

* "Life-threatening" in the definition of "serious" refers to an event in which the subject was at risk of death at the time of the event; it does not refer to an event which hypothetically might have caused death if it were more severe.

** "Hospitalisation" means any unexpected admission to a hospital department. It does not usually apply to scheduled admissions that were planned before study inclusion or visits to casualty (without admission).

Medical judgement should be exercised in deciding whether an adverse event/reaction is serious in other situations. Important adverse events/reactions that are not immediately life-threatening, or do not result in death or hospitalisation but may jeopardise a subject, or may require intervention to prevent one of the other outcomes listed in the definition above should also be considered serious.

7.7. Reporting of SAEs

Rapid reporting, within 24 hours of the Principal Investigator or designee becoming aware of the event, of all SAEs occurring during the study or within 28 days following the completion of the study treatment by the subject, must be performed as detailed in the "SAE reporting instructions". If the investigator becomes aware of safety information that appears to be drug related, involving a subject who participated in the study, even after an individual subject has completed the study, this should also be reported to the Sponsor.

The SAE should be reported electronically to the study team at the Imperial Clinical Trials Unit – Section on Cancer via the RADICAL database as detailed in the Pharmacovigilance study manual.

All SAEs will be reviewed by the Chief Investigator or designated representative to confirm relatedness and expectedness.

Following documented assessment by the CI, the completed SAE form will be sent by e-mail to AstraZeneca and the Sponsor by the study team at ICTU-Ca within the pre-specified timelines.

7.8. Definition of a Serious Adverse Reaction (SAR)

A SAR is defined as a SAE that is judged to be related to any dose of study drug administered to the subject.

7.9. Definition of Suspected Unexpected Serious Adverse Reaction (SUSAR)

Any SAR that is NOT consistent with the applicable product information as set out in the Investigator Brochure (IB) or Summary of Product Characteristics (SPC).

7.10. Reporting of SUSARs

SUSARs will be notified to the appropriate regulatory authority, the relevant Independent Ethics Committee (IEC) / Institutional review board (IRB), AstraZeneca, the Sponsor and the participating Principal Investigators by ICTU-Ca in accordance with regulatory requirements.

Follow up of patients who have experienced a SUSAR should continue until recovery is complete or the condition has stabilised.

7.11. Annual Reporting of Serious Adverse Reactions

Annual reports will be submitted to the MHRA and main REC by ICTU-Ca according to current requirements.

8. STATISTICAL ANALYSES

8.1. Sample Size and Power Considerations

For the primary analysis, a 95% two-sided confidence interval will be calculated for change in tumour size at 12 weeks. With 50 patients, assuming a standard deviation (SD) of 0.30* for the change in log transformed tumour size, the confidence interval for the mean on the log scale will extend 0.083 from the observed mean in either direction. On the natural scale, the 95% confidence interval for the observed geometric mean will extend 1.09 in either direction. This sample size should also be sufficient for the secondary and exploratory analyses to be performed.

*Our estimate of the SD is based on previously collected data, which showed that the standard deviation of logarithmically transformed tumour size at 12 weeks is 0.30. Since we would expect the SD of change in logarithmically transformed tumours size to be somewhat smaller than the SD of log transformed tumour size at 12 weeks, we feel that the above estimate of the width of the confidence interval is very conservative.

8.2. Data Analysis

8.2.1. Interim Analysis

An interim analysis will occur after 20 patients are recruited into the study (including patients in the safety run in phase) and have completed their 12-week follow up. Following recommendations from the Independent Data Monitoring Committee (IDMC) data will also be reviewed once 20 patients (including patients in the safety run in phase) have completed their 20-week follow up. Recruitment into the study will continue whilst the analysis is being carried out.

$\geq 30\%$ will be considered as the 12/20-week clinical benefit rate (stable disease, partial response, complete response) of interest and $\leq 5\%$ as non-significant 12/20-week clinical benefit rate. With power of 85% and type I error of one-sided 0.05, the study will continue if 4 or more patients out of 20 show clinical benefit. If less than 4 patients show clinical benefit the study will only continue if a particular biomarker has been identified.

8.2.2. Preliminary Final Analysis

Since the study has follow up of efficacy and safety endpoints beyond 12 weeks, the preliminary final analysis may be conducted as soon as the database can be soft locked for the primary endpoint data accumulated up to 12 weeks after the last subject enters the study.

The analysis of primary endpoint, i.e. change in tumour size at 12 weeks (or progression if prior to week 12), will be performed on completed cases only. To assess the effect of early drop out (due to death or withdrawal before 12 week follow up scan or progression, for example) change in tumour size at 6 weeks will also be calculated and the results compared to the primary analysis. Subjects with only baseline measures will be excluded from the analysis.

The study data will be summarised using standard descriptive methods. Histograms and box-plots will be used to assess the distributional assumptions and to check for possible outliers. Mathematical transformations will be applied, where appropriate, in order to render variables normally distributed. Continuous variables that follow an approximately normal distribution will be summarised using the mean and standard deviation. Skewed continuous variables will be summarised using the median and inter-quartile range. Categorical variables (binary, ordered and multinomial) will be presented in terms of frequencies and percentages. Where possible, the relationship between the outcomes and other variables will be explored graphically, using scatter plots and box-plots prior to model fitting. Change in tumour size at 12 weeks for each patient will

be shown graphically in a “waterfall plot” with subgroups based on tumour response and objective response highlighted in different colours to identify possible patterns.

The comprehensive statistical analysis plan (SAP) will be finalised prior to preliminary final analysis.

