5.2.21. Tumour Assessments (Phase IIa only)

Tumour assessments will be performed using CT or MRI scans of the chest, abdomen and pelvis. The same method used for assessment at baseline must be used at all subsequent time points.

Tumour assessment will include: if disease is measurable or non-measurable (at least one lesion must be measurable), date of assessment, imaging method used, site (breast, lung, liver, pleural effusion, local lymph nodes, distant lymph nodes, bone, brain or other site), longest diameter of each target lesion and sum of longest diameters for all target lesions.

Patient response to treatment will be assessed using RECIST v1.1 criteria. Tumour size, Progression Free Survival and Objective Response Rate will all be determined.

Tumour Size, will be assessed at baseline and on scans at subsequent time points and recorded as the sum of the longest diameters of the target lesions.

Progression Free Survival (PFS) is defined by the progression criteria of RECIST.

Objective Response Rate (ORR) is defined as the percentage of patients who have at least one visit response of CR or PR prior to any evidence of progression (as defined by RECIST v1.1)

The RECIST v1.1 (January 2009) guidelines for measurable, non-measurable, target and non-target lesions and the objective tumour response criteria (complete response, partial response, stable disease or progression of disease) are detailed in Appendix A

Baseline assessment should be performed no more than 28 days before the start of study treatment and ideally as close as possible to the start of study treatment; it should include all areas known for possible breast cancer metastases.

Subsequent tumour assessments will be conducted at week 6, week 12 (primary endpoint) and then every 8 weeks until objective disease progression or cessation of study treatment and finally at AZD4547 discontinuation visit. The window for each assessment is ± 1 week.

Duplicates will be made of all CT/MRI scans. These duplicate scans will be collected to enable an independent review of progression.

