6.2.6.2. Phase IIa

The intention-to-treat analysis set (ITTS) will be used for the efficacy analysis. The ITTS includes all study patients irrespective of drug compliance to study medication.

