8.2.6. Efficacy Analysis

All patients will be included in the efficacy analysis.

To be considered ‘evaluable’ for the primary efficacy analysis, a patient must have a week 12 (± 1 week) tumour measurement or evidence of progression prior to week 12.

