8.2.7. Primary Analysis

The primary endpoint of change in tumour size at week 12 (or progression if prior to week 12) will be assessed in all patients. The data cut-off for the primary endpoint will occur 12 weeks after the last subject has entered the study.

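### The primary analysis is said to cover all patients but keeps completed cases only, so patients who stop before week 12 without progression are lost, including any with usable scans

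*Protocol*

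**What the plan says.** Three places put every patient in the efficacy analysis. Section 6.2.6.2 assigns efficacy to the intention-to-treat set: "The ITTS includes all study patients irrespective of drug compliance to study medication". Section 8.2.6 states: "All patients will be included in the efficacy analysis". Section 8.2.7 has the primary endpoint assessed in all patients.

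Other places narrow this. Section 8.2.2 says the primary analysis "will be performed on completed cases only" and excludes patients with only baseline measures. Section 8.2.4 allows no imputation in the primary analysis. Section 8.2.6 itself goes on to require a week-12 (±1 week) measurement or evidence of earlier progression before a patient counts as evaluable.

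Under Section 5.2.21, scans are taken at week 6, week 12 and "then every 8 weeks until objective disease progression or cessation of study treatment", with a last one at the AZD4547 discontinuation visit. The 28-day follow-up in Section 3.4 is for safety data.

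On precision, Section 8.1 takes 50 patients and an SD of 0.30 and states that "the confidence interval for the mean on the log scale will extend 0.083 from the observed mean in either direction". On timing, Section 8.2.7 says: "The data cut-off for the primary endpoint will occur 12 weeks after the last subject has entered the study".

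**The concern.** The all-patient statements and the completed-case rule cannot both be followed for the primary endpoint. The protocol itself fixes the completed-case rule, so a later analysis plan could not change it without departing from the protocol.

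The loss comes from the design. Once treatment stops permanently, only the discontinuation-visit scan is left. A patient who stops for toxicity at week 7 without progression may have a week-6 and a discontinuation scan, yet contributes nothing. The same holds for a patient who dies, or who deteriorates without documented progression, before week 12.

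Such losses are foreseeable. Section 8.2.2 itself names death and withdrawal before the week-12 scan as causes of drop-out. Section 1.4 reports that 5 of 12 patients on the same AZD4547 dose and schedule with exemestane left for adverse events, as did 8 of 40 in Part C of the phase I study. It gives no timing for either.

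There is no control arm in which the same selection could cancel out, so any difference between those lost and those kept goes straight into the estimated mean.

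**Working it through.** **1. The plan's own figure.** Section 8.1 gives n = 50, an SD of 0.30 on the log scale, and a 95% two-sided interval.

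Half-width = 1.96 × 0.30 / √50 = 0.0832, and exp(0.0832) = 1.087. This reproduces the stated 0.083 and 1.09. It is the normal-quantile value with all 50 patients analysed. With the t quantile on 49 degrees of freedom it is 0.0853, a factor of 1.089.

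**2. Who is in the analysis.** Reading Sections 5.2.21, 8.2.2, 8.2.4 and 8.2.6 together:

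- Week-12 scan within the window: kept.
- Evidence of progression before week 12: kept.
- Permanent stop, deterioration or death before week 12, no evidence of progression, with a week-6 or discontinuation scan: dropped.
- As the line above, but with baseline measures only: dropped.

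**3. Precision by evaluable number.** Half-width = quantile × 0.30 / √n. The last column is the SD of change at which the normal-quantile half-width is still 0.083, that is 0.083 × √n / 1.96. Section 8.1 gives no non-evaluable rate, so the range is assumed.

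| Evaluable n | Share lost | Half-width, normal | Half-width, t | SD that restores 0.083 |
|---|---|---|---|---|
| 50 | 0% | 0.083 | 0.085 | 0.299 |
| 45 | 10% | 0.088 | 0.090 | 0.284 |
| 40 | 20% | 0.093 | 0.096 | 0.268 |
| 35 | 30% | 0.099 | 0.103 | 0.251 |
| 30 | 40% | 0.107 | 0.112 | 0.232 |

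With the t quantile, the restoring SD at 40 evaluable is 0.260.

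**4. Bias of the completed-case mean.** Bias = share missing × (mean log change in those lost minus that in those kept). The document gives neither input. For illustration, take a gap of log(1.2) = 0.182, the size of a 20% increase:

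- 10% missing: 0.10 × 0.182 = 0.018, or 21% of the normal half-width at that n.
- 20% missing: 0.036, or 39%.
- 30% missing: 0.055, or 55%.
- 40% missing: 0.073, or 68%.

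If the gap is zero, so is the bias.

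**5. Cut-off.** Assessment days count from Cycle 1 Day 1 (Section 5.1), and the week-12 scan may be taken up to a week late (Section 5.2.21), so a valid scan can fall 13 weeks after Cycle 1 Day 1. The cut-off is 12 weeks after the last patient enters. Section 7.2 has the study-entry form completed when eligibility is confirmed. Entry may then precede Cycle 1 Day 1, which would widen the shortfall beyond one week.

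**The case against.** Much of the opposing case stands.

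- **Failures are mostly kept.** A reader might infer that clinical failures drop out as a class. They do not, because evidence of progression before week 12 makes a patient evaluable. The discontinuation scan can supply that evidence or fall within the week-12 window. Appendix A asks for every effort to document progression after symptomatic deterioration, and Section 5.1 keeps RECIST assessments going through temporary breaks. The gap is confined to permanent stops and deaths with no evidence of progression.
- **Direction is not shown.** A reader might infer that the result is known to lean favourable. Patients who stop for toxicity need not have worse tumour change. One could take 20% missing and a gap of 0.3, giving a bias of 0.06 and interval coverage near 76%. That arithmetic is right, but neither input comes from the protocol. Documented progressors are kept, so progression is also an imperfect benchmark for those lost. Section 3.2 describes the schedule as well tolerated in this trial's run-in.
- **The ±0.083 is not an error.** It reproduces at n = 50, and Section 8.1 calls the width very conservative because the SD of change should be below 0.30.
- **The mean is not the only result.** The interim rule uses clinical benefit rate, and response and PFS are also reported.
- **Some provision exists.** Section 8.2.2 plans a week-6 comparison, and Section 8.2.4 permits imputation in sensitivity analyses. The cut-off affects only the last few patients, and Section 8.2.3 adds later data at the final analysis.

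What does not stand is that these provisions repair the primary analysis. The week-6 comparison mixes the effect of time with that of drop-out and misses anyone who leaves before week 6. Sensitivity imputation is optional. The conflict over the population remains.

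**Conclusion.** The point holds in limited form. The protocol states two incompatible populations for its primary analysis, and the operative rule discards observed scans from patients who leave before week 12 without evidence of progression.

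The mean can be biased by 0.02-0.07 on the log scale, if 10-40% are missing and the gap is 0.18. Both are assumptions, and the lower limit is zero if there is no gap. A favourable lean is plausible for deaths and deterioration but cannot be established from the document.

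The precision loss is modest. At SD 0.30 the t-based factor goes from 1.089 at 50 evaluable to 1.109 at 35. An SD of change near 0.27 (0.268 normal, 0.260 t) would restore ±0.083 at 40 evaluable. The cut-off mismatch is real but small. The stated precision is best described as not assured, rather than wrong.

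**What to change.** - Reconcile Sections 6.2.6.2, 8.2.6 and 8.2.7 with Section 8.2.2, so that one population is named for the primary analysis.
- Make the primary analysis a longitudinal model of log(sum of diameters / baseline) in all patients with at least one post-baseline scan, using week-6 and discontinuation-visit scans. For patients who progress before week 12, carry the value at the progression scan as the week-12 value, in line with the stated endpoint.
- Keep completed cases as a sensitivity analysis.
- Add a supporting worst-value analysis that includes patients who die or clinically progress without a scan. The model alone would still omit patients with baseline measures only.
- Set the cut-off at 13 weeks after the last patient's Cycle 1 Day 1.
- Restate Section 8.1 by expected evaluable number: about ±0.085, 0.090, 0.096 and 0.103 for 50, 45, 40 and 35 at SD 0.30.

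The cost is protocol wording, a little programming, a slightly wider stated interval and a short delay to lock. No scans beyond those planned are needed. The model rests on a missing-at-random assumption, which the data cannot confirm; the worst-value analysis shows how much depends on it.

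### The early-dropout check sets week 6 change against the completed-case week 12 result, so it mixes change over time with selection by dropout

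*Protocol*

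**What the plan says.** Section 8.2.2 (Preliminary Final Analysis) says the analysis of the primary endpoint, change in tumour size at 12 weeks or progression if earlier, "will be performed on completed cases only". It then gives a purpose, "To assess the effect of early drop out (due to death or withdrawal before 12 week follow up scan or progression, for example"), and a method: "change in tumour size at 6 weeks will also be calculated and the results compared to the primary analysis". It adds: "Subjects with only baseline measures will be excluded from the analysis".

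Other sections bear on this:

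- Section 8.2.6 counts a patient as evaluable with a tumour measurement at week 12 (± 1 week) or evidence of progression before week 12.
- Section 8.2.4 rules out imputation in the primary analysis. It says imputation may be proposed for sensitivity analysis, with details in the SAP if so.
- Section 2.4 lists week 6 change as a secondary endpoint in its own right.
- Section 5.2.21 schedules scans at weeks 6 and 12, then every 8 weeks until progression or the end of study treatment, with a last scan at the AZD4547 discontinuation visit.

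**The concern.** The sentence names a purpose and fixes a method, and the method does not isolate what the purpose asks for. The week 6 summary includes patients who later leave; the week 12 summary does not. The first describes 6 weeks of treatment, the second 12. A difference can therefore arise with no dropout effect, and a real dropout effect can be cancelled by growth between the visits.

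The trial has one arm and an unimputed completed-case primary analysis, so no control group offsets selection. Leaving treatment without progression is plausible: section 1.4 reports that 5 of 12 patients stopped for adverse events in the exemestane combination cohort on 80 mg bd, one week on and one week off (timing not given). A patient who stops for toxicity between the two scheduled scans can have a week 6 value and no week 12 value. The risk is a false reassurance or a false alarm about the primary estimate.

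**Working it through.** **Inputs from the protocol (section 8.1).** The primary analysis is an interval estimate: "For the primary analysis, a 95% two-sided confidence interval will be calculated for change in tumour size at 12 weeks". Its precision is set out as "With 50 patients, assuming a standard deviation (SD) of 0.30* for the change in log transformed tumour size", giving that "the confidence interval for the mean on the log scale will extend 0.083 from the observed mean in either direction".

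**The plan's own figure.** Half-width = 1.96 × 0.30 / √50 = 0.083, and exp(0.083) = 1.09. Both stated figures are reproduced. They give a sense of scale only: 0.083 is the half-width for one mean, not for the difference considered here.

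**What the planned comparison measures.** Let W6 and W12 be log change at weeks 6 and 12. Let *all* be the patients with a week 6 scan, and *c* those of them with a week 12 value.

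Gap = mean(W12, c) − mean(W6, all)

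= [mean(W12, c) − mean(W12, all)] + [mean(W12, all) − mean(W6, all)]

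The first bracket is the bias from dropout. The second is the average change between the visits. It involves the unseen week 12 values of those who left, so it cannot simply be subtracted. The gap equals the bias only if the second bracket is zero. No assumed number enters this step.

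**Gap with no dropout.** If log change is steady over 12 weeks and the 12-week change is g, the gap is log(1 + g) / 2:

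- g = +10%: 0.048
- g = +20%: 0.091
- g = −20%: −0.112

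**A masked effect (assumed values).** Suppose 20% leave after week 6 with a 12-week log change of +0.30, completers have +0.05, and change is steady.

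- True week 12 mean: 0.8 × 0.05 + 0.2 × 0.30 = 0.10
- Week 6 mean, all: 0.10 / 2 = 0.05
- Week 12 mean, completers: 0.05
- Gap: 0.05 − 0.05 = 0, while the bias is 0.05 − 0.10 = −0.05

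At week 6 itself, leavers are at 0.15 and completers at 0.025. A same-visit comparison shows that difference of 0.125.

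**Simulation.** One million patients per row, with assumed SD 0.20 at week 6, correlation 0.8 between visits and the protocol's SD 0.30 at week 12. In the informative rows, patients with more growth at week 6 are likelier to leave. The same-visit column is mean(W6, c) − mean(W6, all). Early progression is not modelled.

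| Mean at week 6 / 12 | Dropout | Planned gap | Same-visit | True bias |
|---|---|---|---|---|
| −0.05 / −0.10 | none | −0.050 | 0.000 | 0.000 |
| −0.05 / −0.10 | 20% random | −0.050 | 0.000 | 0.000 |
| +0.05 / +0.10 | 20% informative | −0.004 | −0.045 | −0.054 |
| −0.05 / −0.10 | 20% informative | −0.105 | −0.046 | −0.055 |
| 0 / 0 | 20% informative | −0.054 | −0.045 | −0.054 |

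The planned gap matches the bias only in the last row, where mean change is the same at both visits. The same-visit contrast responds to selection and not to the time trend, though it does not reproduce the week 12 bias exactly.

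**The case against.** Several points on the other side stand.

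- **Other safeguards are possible.** A reader might infer that this check is the only protection against dropout. Section 8.2.4 does not support that: it lets the SAP add imputation-based sensitivity analyses. These are optional and would not repair this comparison, so it is fair to say only that no other check is committed to.
- **Progression is largely kept.** Progression before week 12 makes a patient evaluable, and a scan is due at the discontinuation visit. A patient who progresses on the week 6 scan may contribute that scan to both summaries, which narrows the time gap. What remains is mainly death or withdrawal without documented progression.
- **The masking example is demanding.** At a steady 0.30 / 12 = 0.025 log per week, its leavers reach +20% (0.182 log) at about week 7.3. With a 5 mm increase that is progression under Appendix A. The example needs them to leave with no scan showing it.
- **The larger gaps are extreme.** Section 8.2.8 expects a median time to progression of 6 months. If a typical patient reaches +20% at 26 weeks, the 12-week change is 0.182 × 12 / 26 = 0.084 and the gap about 0.042, close to the +10% case.
- **No statistic or decision rule is fixed.** The SAP could present week 6 change by completion status. But the protocol's sentence specifies a comparison with the primary analysis, and that is what needs correcting.

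**Conclusion.** The point holds. As worded, the check cannot separate dropout from time on treatment, and it equals the dropout effect only if mean change is the same at weeks 6 and 12. That follows from the algebra alone.

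The size is not known. The protocol gives no dropout rate, no week 6 SD and no correlation between visits, so every magnitude above is illustrative. A gap of about 0.05 log with no dropout, for a steady 12-week change of +10%, is a reasonable guide.

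A reader might go further and infer that the primary estimate is biased, or that the check is bound to mislead. The documents do not support either: early progressors stay in the analysis, and the number lost without progression could be small. Sample size and the primary estimate are unaffected, and week 6 change remains sound as a secondary endpoint. The wording should be changed because a stated method does not serve its stated purpose and the replacement costs almost nothing.

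**What to change.** In section 8.2.2, replace the comparison with text to this effect: change in log tumour size at week 6 will be summarised for patients with an evaluable primary value (week 12 measurement or earlier progression) and for those without one, and the difference reported with a 95% confidence interval; the number of patients with no post-baseline scan will be reported, with reasons, and the check does not speak to them.

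Optionally, add a sensitivity estimate of the week 12 mean from all available scans, by a repeated-measures model or imputation. Early progressors must be handled as in the primary endpoint; otherwise it will differ from the primary result for reasons other than dropout. State the missing-at-random assumption. Keep week 6 change as a secondary endpoint.

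The cost is a wording change and a small extra analysis of data already collected. The weakness is precision. With 10 patients lacking a primary value and 40 having one, and an assumed week 6 SD of 0.20 to 0.30, the half-width is 1.96 × SD × √(1/10 + 1/40), or 0.139 to 0.208. It should be read as an estimate, not a test; a wide interval is not evidence that dropout is harmless.
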